4.6.2. Nodule Size by Caliper Measurement

Nodule size (ie, length and width) will be determined by handheld calipers and will be assessed for each treated nodule.

The size of nodule will be the larger of either nodule length or nodule width.

The area of nodule will be calculated as:

Area of the Nodule = (Nodule Width * Nodule Length * pi)/4 where pi=22/7

The nodule level data will be summarized by categories of nodule size, treatment group and visit. Only treated nodules will be included for data analyses and summarized at participant level. The change from Baseline (Day 1) in nodule size at EOS (Day 57) and other post baseline visits will be analyzed.

4.6.3. Nodular Hardness by Durometer Assessment

Nodule hardness will be quantified using durometer and will be assessed for each treated nodule. The nodule level data will be summarized by treatment and visit, the change from Baseline (Day 1) in nodule hardness at EOS (Day 57) and other post baseline visits of the treatment will be analyzed. The average of all treated nodule hardness will be used for data analyses and summarization at participant level.

4.6.4. Number of Nodules

The number of treated nodules will be based study intervention data from eCRF. Foot level data will be summarized by categories of nodule size, treatment group, and visit. The total number of nodules by foot will be used for data analyses and summarization at participant level. In addition, all nodules that were assessed by foot will be listed.

4.7. Participant Reported Outcome Assessments

The FFI, PGIS, PGIC and NRS assessment will be captured on a participant level. The Subject Satisfaction Scale will be captured at the foot level.

4.7.1. Foot Function Index

4.7.1.1. Pain Subscale

The participant will assess the foot pain using a 5-point scale ranging from 0 (“None”) to 4 (“Extreme”) at each visit as per the SoA ([Table 2](#)).

4.7.1.2. Difficulty Subscale

The participant will assess the difficulty of feet when performing the activities using a 5-point scale ranging from 0 (“No difficulty”) to 4 (“A lot of difficulty”) at each visit as per the SoA ([Table 2](#)).

4.7.1.3. Activity Limitation Subscale

The participant will assess the activity limitation of feet using a 5-point scale ranging from 0 (“Never”) to 4 (“Always”) at each visit as per the SoA ([Table 2](#)).

4.7.1.4. Subscale Score and Individual Item Scores on FFI

The impact of the selected nodule(s) will be assessed using the FFI, which is a foot function assessment instrument. The FFI is comprised of 21 items and is used to assess Pain, Difficulty and Activity limitation.

The subscale score (%) is calculated by adding the answered item scores and dividing by the sum of the maximum score of the items answered.

The calculation is:

$$\text{Subscale score (\%)} = \frac{\text{Sum of answered item scores}}{\text{Sum of maximum score of answered items}} \times 100$$

The maximum total score of each subscale if all items answered is given as below:

- Activity limitation subscale (3 items) with a maximum total score of 12
- Difficulty subscale (9 items) with a maximum total score of 36
- Pain subscale with Orthotics (9 items) with a maximum total score of 36 **OR**
- Pain subscale without Orthotics (7 items) with a maximum total score of 28

Total subscale score is defined as the sum of the scores of answered items in each subscale (ie, Pain subscale, Difficulty subscale, and Activity limitation subscale). In addition, the total pain subscale score will be normalized by a multiplying factor of 9/7 for participants who have answered ‘No’ or didn’t answer the questions related to orthotics use. The normalized total pain subscale score will be utilized for analyses and for calculating the total composite score and total combined score.

4.7.1.5. Composite Score on FFI

The composite score on FFI is defined as the weighted average of *i* subscale scores (%) (ie,, Activity Limitation subscale, Difficulty subscale, and Pain subscale), with number of answered items as a weighted average.

The calculation is:

$$\text{Composite score (\%)} = \frac{\sum_{i=1}^3 [\text{Subscale score (\%)} (i) \times \text{Number of answered items in the subscale}(i)]}{\sum_{i=1}^3 \text{Number of answered items in the subscale}(i)}$$

where, *i*=1, 2, 3 (for each subscale score (%)).

For participants who have answered ‘No’ or didn’t answer the questions related to orthotics use, the number of answered items in the pain subscale will be normalized by a multiplying factor of 9/7.

The Total Composite Score is defined as the sum of all total subscale scores (Activity Limitation subscale, Difficulty subscale, and Pain subscale).

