
 To assess the safety and tolerability of EN3835 in participants with plantar fibromatosis. 	
 Safety of EN3835 as assessed by incidence, severity and duration of treatment-emergent adverse events (TEAEs), adverse events of special interest (AESIs), and serious adverse events (SAEs). The change from baseline in vital signs and clinical laboratory values at each visit where these parameters are measured.

 To assess the immunogenicity of EN3835 in participants with plantar fibromatosis. 	
 Presence of anti-AUX-I and anti-AUX-II antibody titer levels in EN3835 treated-participants at Day 1 and Day 57. Presence of neutralizing antibodies to AUX-I and AUX-II in EN3835 treated-participants at Day 1 and Day 57.
Exploratory	

 To assess the overall improvement in the FFI composite score with EN3835 vs placebo. 	
 The difference between EN3835 and placebo in the mean change from Baseline (Day 1) to Day 57 on the FFI composite score, with the score of each of the 21 items ranging from 0 to 4, with 4 indicating higher severity. The mean change from Baseline (Day 1) to Days 15, 29, 43, and 57 on the FFI composite score with EN3835 vs placebo.

 To assess the overall improvement in severity of plantar fibromatosis on the Patient Global Impression of Severity (PGIS) PF Overall scale. 	
 The difference between EN3835 and placebo at Day 57 on the PGIS PF Overall score. The difference between EN3835 and placebo Days 15, 29, 43, and 57 on the PGIS PF Overall score with EN3835 vs placebo.

 To assess the overall improvement in the severity of foot pain with EN3835 vs placebo in the PGIS foot pain subscale. 	
 The difference between EN3835 and placebo at Day 57 on the foot pain subscale of the PGIS. The difference between EN3835 and placebo at Days 15, 29, 43, and 57 on the PGIS foot pain subscale, ranging from 0 ("None") to 4 ("Severe") with EN3835 vs placebo.

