
 To assess the safety and tolerability of EN3835 in participants with plantar fibromatosis. To assess the immunogenicity of EN3835 in participants with plantar fibromatosis. 	
 Safety of EN3835 as assessed by incidence, severity, and duration of treatment-emergent adverse events (TEAEs), adverse events of special interest (AESIs), and serious adverse events (SAEs). The change from baseline in vital signs and clinical laboratory values at each visit where these parameters are measured. Presence of anti-AUX-I and anti-AUX-II antibody titer levels in EN3835 treated-participants at Day 1 and Day 57. Presence of neutralizing antibodies to AUX-I and AUX-II in EN3835 treated-participants at Day 1 and Day 57.

Table 1: Objectives and Endpoints (Continued)

Objective	Endpoint
Exploratory	

 To assess the overall improvement in the FFI total score with EN3835 vs placebo 	
 The difference between EN3835 and placebo in the mean change from Baseline (Day 1) to Day 57 on the FFI total score of 21 items with the score of each item ranging from 0 to 4, with 4 indicating higher severity. The mean change from Baseline (Day 1) to Days 15, 29, 43, and 57 on the FFI total score with EN3835 vs placebo.

 To assess the overall improvement in severity of plantar fibromatosis on the Patient Global Impression of Severity (PGIS) PF Overall scale. 	
 The difference between EN3835 and placebo at Day 57 on the PGIS PF Overall score. The difference between EN3835 and placebo Days 15, 29, 43, and 57 on the PGIS PF Overall score with EN3835 vs placebo.

 To assess the overall improvement in the severity of foot pain with EN3835 vs placebo in the PGIS foot pain subscale 	
 The difference between EN3835 and placebo at Day 57 on the foot pain subscale of the PGIS. The difference between EN3835 and placebo at Days 15, 29, 43, and 57 on the PGIS foot pain subscale, ranging from 0 (“None”) to 4 (“Severe”) with EN3835 vs placebo.

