4.7.1.6. Pain and Difficulty Combined Score on FFI

The Combined score on the Pain and Difficulty subscale is defined as the weighted average of *i* subscale scores (%) (ie, Pain and Difficulty subscale), with the number of answered items used in calculating a weighted average.

The calculation is:

$$\text{Combined score (\%)} = \frac{\sum_{i=1}^2 [\text{Subscale score (\%)} (i) \times \text{Number of answered items in the subscale}(i)]}{\sum_{i=1}^2 \text{Number of answered items in the subscale}(i)}$$

where, $i=1, 2$ (for each subscale score (%)). For participants who have answered ‘No’ or didn’t answer the questions related to orthotics use, Number of answered items in the pain subscale will be normalized by a multiplying factor of 9/7.

The Total Combined (Pain and Difficulty) Score is defined as the sum of both total subscale scores.

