6.2.1. Derivation of Efficacy Parameter

Table 26 provides detailed information for the efficacy parameters as per eCRF/Vendor data collection. The derivation of these parameters is added on a participant-level, foot-level, and nodule-level.

Table 26: Efficacy Parameter Data

SN	Category	Parameter	Participant Level	Foot Level	Nodule Level	Derivation for Participant Level	Derivation for Foot Level	Derivation for Nodule Level
1	FFI	FFI Total Score	√			Section 4.7.1.4	NA	NA
2	FFI	FFI Pain Subscale Score	√			Section 4.7.1.4	NA	NA
3	FFI	FFI Difficulty Subscale Score	√			Section 4.7.1.4	NA	NA
4	FFI	FFI Pain & Difficulty combined score	√			Section 4.7.1.6	NA	NA
5	FFI	FFI Activity Limitation subscale score	√			Section 4.7.1.4	NA	NA
6	FFI	FFI Composite Score	√			Section 4.7.1.6	NA	NA
7	NRS	Pain intensity NRS	√			Section 4.7.4	NA	NA
8	Nodule	Nodule size by Caliper measurement	√		√	Section 4.6.2	NA	eCRF data
9	Nodule	Nodule Hardness by Durometer measurement	√		√	Section 4.6.3	NA	eCRF data
10	Nodule	Number of Nodules treated	√		√	Section 4.6.4	NA	eCRF data
11	Nodule	Nodular Consistency	√		√	Section 4.6.1	NA	eCRF data
12	PGIS	PGIS Overall Severity	√			Vendor data	NA	NA
13	PGIS	PGIS Pain Subscale	√			Vendor data	NA	NA
14	PGIS	PGIS Difficulty Subscale	√			Vendor data	NA	NA
15	PGIS	PGIS Activity Limitation subscale	√			Vendor data	NA	NA
16	PGIC	PGIC Overall Severity	√			Vendor data	NA	NA
17	PGIC	PGIC Pain Subscale	√			Vendor data	NA	NA
18	PGIC	PGIC Difficulty Subscale	√			Vendor data	NA	NA
19	PGIC	PGIC Activity Limitation Subscale	√			Vendor data	NA	NA
20	CGIC	Clinician Global Impression of Change Scale		√		Section 4.8.1	eCRF data	NA
21	SSTS	Subject Satisfaction with Treatment Scale		√		Section 4.8.1	eCRF data	NA

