3 rd Key Secondary	The difference between EN3835 and placebo in the mean change from Baseline (Day 1) to the Day 57 in the nodular hardness of the treated nodules by durometer measurements.	ANCOVA (ITT)-Participant level analyses	ANCOVA (ITT)-Participant level analyses	
 • MMRM based on (Observed Data) (ITT) • MMRM based on TPA (ITT) 	
 • ANCOVA (FAS) • ANCOVA (mITT) • Nodule level analyses - MMRM (Observed Data) (ITT) • Nodule level analyses - MMRM (TPA) (ITT)
Secondary	The mean change from Baseline (Day 1) to Days 15, 29, 43, and 57 on the pain subscale of the FFI (total score on 9 items), ranging from 0 (“None”) to 4 (“Extreme”) with EN3835 vs placebo.	MMRM based on (Observed Data) (mITT)			
Secondary	The mean change from Baseline (Day 1) to Days 15, 29, 43, and 57 on the total combined score of the pain and difficulty subscales of the FFI with EN3835 vs placebo.	MMRM based on (Observed Data) (mITT)			
Secondary	The difference in the proportion of EN3835-treated participants and those receiving only placebo reporting “Minimally Improved” (+1) “Much Improved” (+2) or “Very Much Improved” (+3) on the Clinician Global Impression of Change Scale, a 7-point scale ranging from -3 (“Very Much Worse”) to +3 (“Very Much Improvement”) at Day 15, 29, 43 and 57.	Cochran-Mantel-Haenszel method (mITT)			
Secondary	The mean change from Baseline (Day 1) to Days 15, 29, 43, 57 in the nodular hardness of the treated nodules by durometer measurements with EN3835 vs placebo	MMRM based on (Observed data) (mITT)			Nodule level analyses - MMRM (Observed Data) (mITT)
Exploratory	The difference between EN3835 and placebo in the mean change from Baseline (Day 1) to Days 15, 29, 43, and 57 on the FFI total score of 21 items with the score of each item ranging from 0 to 4, with 4 indicating higher severity.	MMRM based on (Observed data) (mITT)			

Table 27: List of Analyses Performed on All Efficacy Endpoints (Continued)

Endpoint (Primary/ Secondary /Exploratory)	Endpoint	Primary analyses	Subgroup Analyses	Sensitivity Analyses	Supportive Analyses
Exploratory	The difference between EN3835 and placebo at Day 57 on the PGIS PF Overall score at Days 15, 29, 43, and 57 on the PGIS PF Overall score, ranging from 0 (“None”) to 4 (“Severe”).	Wilcoxon rank-sum test & H-L estimator (mITT)			

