Exploratory	The difference between EN3835 and placebo in the mean change from Baseline (Day 1) to Days 15, 29, 43, and 57 on the FFI composite score, with the score of each of the 21 items ranging from 0 to 4, with 4 indicating higher severity.	MMRM based on (Observed Data) (mITT)			

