7.6.4. Exploratory Analyses

7.6.4.1. FFI Composite Score

The mean change from Baseline (Day 1) to Days 15, 29, 43, and 57 on FFI total composite score with EN3835 vs placebo and their treatment differences will be estimated using the similar statistical model based on observed data using MMRM (Section 7.6.1.3).

The LSM estimate for the mean change from baseline on FFI total composite score at each visit for each treatment group and the LSM for treatment difference at each visit and their 95% confidence interval (CI) will be presented.

The descriptive statistics for observed and change from baseline on the composite score on FFI by visit and treatment group will be provided.

A listing of the FFI total score (derived) by participant will be provided.

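### The SAP still analyses the FFI total score that the protocol has replaced, and its derivation table points the FFI composite to the pain-and-difficulty section

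*SAP*

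**What the plan says.** **Protocol.** Section 4 (and the synopsis) has one exploratory objective for the whole instrument: "To assess the overall improvement in the FFI composite score with EN3835 vs placebo". Its endpoints are the change to Day 57 and the changes to Days 15, 29, 43 and 57. No FFI total score appears among the current objectives.

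**SAP, basis.** Section 8 says the SAP is based on Amendment 04. Table 28 declares one change from the protocol, the classification of prior medications, and none to this endpoint.

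**SAP, endpoint tables.** Table 1 gives the objective as "To assess the overall improvement in the FFI total score with EN3835 vs placebo" and does not list the composite. Table 27 has two exploratory rows, one "on the FFI total score of 21 items with the score of each item ranging from 0 to 4" and one "on the FFI composite score, with the score of each of the 21 items ranging from 0 to 4". Both are MMRM on observed data in the mITT population.

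**SAP, derivations.** Section 4.7.1.5 defines a percentage composite over three subscales and then a points version: "The Total Composite Score is defined as the sum of all total subscale scores". Section 4.7.1.6 covers two subscales only: "The Combined score on the Pain and Difficulty subscale is defined as the weighted average of" pain and difficulty. In Table 26, row 6, "FFI Composite Score", cites Section 4.7.1.6, as does row 4, the combined score. Row 1, the FFI total score, cites Section 4.7.1.4.

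**SAP, analysis text.** In Section 7.6.4.1 the MMRM is on the total composite score. The summary sentence reads "The descriptive statistics for observed and change from baseline on the composite score on FFI by visit and treatment group will be provided". The listing is of a derived FFI total score.

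**The concern.** Table 26 is the SAP's map from each efficacy variable to its derivation, and Table 27 is the list of analyses to be run. Someone working from those tables meets two problems.

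First, the composite's pointer leads to a formula without the activity-limitation items. The variable produced would be the pain-and-difficulty score, already analysed as key secondary endpoint 1, under the composite's label.

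Second, Table 27 asks for an analysis of a score that the current protocol does not contain. The section cited for it, 4.7.1.4, defines totals for each subscale but no total over the 21 items.

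At stake is whether the one whole-instrument result in the study report is what the protocol names, and whether a second result appears beside it without a definition.

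**Working it through.** The plan states no figure for this point, so there is none to reproduce. The check sets the SAP's definitions side by side and scores them.

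**Inputs** (SAP Sections 4.7.1.4 to 4.7.1.6). Items are scored 0 to 4. Activity limitation has 3 items (maximum 12), difficulty 9 (maximum 36), and pain 9 with orthotics (maximum 36) or 7 without (maximum 28). Without orthotics the pain total is multiplied by 9/7, and the pain item count used as a weight is multiplied by 9/7 as well. Write A and D for the activity-limitation and difficulty totals and P* for the normalised pain total.

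**Step 1: maxima.**
- Total Composite Score (4.7.1.5): 12 + 36 + 36 = 84.
- Score reached through Table 26 row 6 (4.7.1.6): 36 + 36 = 72.
- Points omitted: 84 − 72 = 12, and 12/84 = 14.3%. This is the whole activity-limitation domain.
- Un-normalised 21-item total without orthotics: 28 + 36 + 12 = 76.

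**Step 2: percentage against points composite.** With all applicable items answered, a subscale percentage times its item count is 100 × S/(4n) × n = 25 × S. For pain without orthotics it is 100 × S/28 × 9 = 25 × S × 9/7 = 25 × P*. So

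Composite (%) = 25 × (A + D + P*)/21 = Total Composite × 100/84.

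The factor is 100/84 = 1.19. Scoring 20,000 simulated complete questionnaires, with and without orthotics, gave a largest discrepancy of 0.0001, which is rounding.

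**Step 3: a constructed participant without orthotics.** Every pain item goes from 3 to 2, difficulty stays at 2, and every activity-limitation item goes from 3 to 1.

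| Score | Baseline | Follow-up | Change |
|---|---|---|---|
| Total Composite, 4.7.1.5 | 27 + 18 + 9 = 54 | 18 + 18 + 3 = 39 | −15 |
| Composite (%), 4.7.1.5 | 64.3 | 46.4 | −17.9 |
| Un-normalised total | 21 + 18 + 9 = 48 | 14 + 18 + 3 = 35 | −13 |
| Combined points, 4.7.1.6 | 27 + 18 = 45 | 18 + 18 = 36 | −9 |
| Combined (%), 4.7.1.6 | 62.5 | 50.0 | −12.5 |

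The Table 26 route loses the 6-point activity-limitation change: −15 + 6 = −9.

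**Step 4: the FFI total score row in Table 27.** There are two readings.
- If the total is built from the normalised subscale totals, it equals the Total Composite Score. The two rows are then one analysis.
- If it is un-normalised, it differs from the Total Composite for every participant without orthotics who has a non-zero pain score (−13 against −15 above). It is then a separate variable that the SAP does not define.

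**Step 5: unanswered items.** With no orthotics, pain items at 3, eight of nine difficulty items answered at 2, and activity limitation at 1, the percentage composite is 25 × (27 + 16 + 3)/(9 + 8 + 3) = 57.5. The Total Composite is 46, and 46/84 = 54.8%. The two forms diverge only when an applicable item is unanswered.

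**The case against.** The strongest reply is that this is a cross-reference slip that would be caught. Section 4.7.1.5 carries the composite's name and stands directly before the section wrongly cited. The SAP separates composite from combined in Section 4.7.1.4, in the baseline rows of Table 21 and in rows 4 and 6 of Table 26 itself. The MMRM in Section 7.6.4.1 uses a term defined only in Section 4.7.1.5. SAS code and table shells are in SAP Module 2, which is not part of these documents, so the programmed derivation is unknown. All of this stands. A reader might infer that the composite will be mis-derived; the documents support only that Table 26, taken literally, leads there.

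A reader might also infer that one result will certainly appear twice with the same p-value. That holds only if the total uses normalised pain. Section 4.7.1.4 makes this the likelier reading, since it says the normalised score is used for analyses, but the SAP gives no formula for the total.

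A third tempting inference is that Section 7.6.4.1 mixes scales in a way that affects the result. Its summary sentence may be shorthand for either form. Reporting percentage and points together is also the SAP's practice for pain (Section 7.6.1.2). With all applicable items answered the forms are exact rescalings, so the p-value is the same. Electronic completion should make unanswered items uncommon. What remains is a labelling problem.

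None of this explains why Table 1 names a score that the current protocol does not, or why Table 27 has a row for it.

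**Conclusion.** The point holds as a correction of the SAP's text. Tables 1 and 27 carry a score that the current protocol does not name, and Table 26 sends the composite to a two-subscale formula and the total to a section that does not define it. This rests on current text in both documents, not on the protocol's amendment log.

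If Table 26 is followed, the loss is 12 of 84 points (14.3%). That is a share of the maximum score and a worst case, not an estimate of bias in any result. The extra Table 27 row is either redundant or undefined, depending on the 9/7 normalisation.

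The consequence is small. Section 6.5 of the SAP gives exploratory endpoints nominal p-values outside the testing hierarchy, so the primary test, the key secondary tests and the sample size are unaffected. The documents give no reason to move the MMRM to the percentage scale. The primary analysis, key secondary 1 and Section 7.6.4.1 all use points, and the protocol does not specify a percentage.

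**What to change.** Before database lock:

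- **Table 1:** replace the FFI total score with the FFI composite score, in the objective and its endpoints.
- **Table 26:** point row 6 to Section 4.7.1.5 and delete row 1.
- **Table 27:** delete the FFI total score row.
- **Section 7.6.4.1:** name the Total Composite Score (points, 0 to 84), which the MMRM already uses, as the endpoint. Use that name in the descriptive table and the listing. If the percentage composite is kept, label it as a supplementary display.
- **Section 7.6.1.2:** make the total-score wording in the listing match.

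The cost is text edits in five places, with a check that the Module 2 shells and code agree. No new data are needed, and there is one analysis fewer.

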4.7.1.6. Pain and Difficulty Combined Score on FFI

The Combined score on the Pain and Difficulty subscale is defined as the weighted average of *i* subscale scores (%) (ie, Pain and Difficulty subscale), with the number of answered items used in calculating a weighted average.

The calculation is:

$$\text{Combined score (\%)} = \frac{\sum_{i=1}^2 [\text{Subscale score (\%)} (i) \times \text{Number of answered items in the subscale}(i)]}{\sum_{i=1}^2 \text{Number of answered items in the subscale}(i)}$$

where, $i=1, 2$ (for each subscale score (%)). For participants who have answered ‘No’ or didn’t answer the questions related to orthotics use, Number of answered items in the pain subscale will be normalized by a multiplying factor of 9/7.

The Total Combined (Pain and Difficulty) Score is defined as the sum of both total subscale scores.

